#### **7.7.1.1 Dose Modifications for Overlapping Toxicities**

Thrombocytopenia and neutropenia are potential overlapping toxicities for selinexor with pomalidomide. If a patient experiences drug-induced thrombocytopenia or neutropenia while receiving the combination under investigation in this study, the Investigator should attempt to determine which drug may be responsible and treat appropriately, including dose modifications, as necessary. If the cause cannot be attributed to a single drug, suggested management strategies for possibly drug-induced thrombocytopenia and neutropenia Grade 3/4 events are provided below.

#### **7.7.1.2 Thrombocytopenia**

1. Grade  $\geq$  2: Hold/adjust selinexor dose as described in Table 4, under Thrombocytopenia.
2. Grade  $\geq$  3: Hold/adjust pomalidomide dose as described in Table 4, under Thrombocytopenia.

#### **7.7.1.3 Neutropenia**

1. Grade 3 without fever: Reduce selinexor by 1 dose level and consider supportive care as described in Table 4, under Neutropenia.
2. Grade 4 without fever: Hold selinexor until ANC returns to Grade  $\leq$  2. Reduce selinexor by 1 dose level. See additional supportive care in Table 4, under Neutropenia.
3. Grade  $\geq$  3 with fever: Hold selinexor until ANC returns to Grade  $\leq$  2, fever resolves, and patient is clinically stable. Reduce selinexor by 1 dose level. See additional supportive care in Table 4, under Neutropenia.
4. Grade  $\geq$  3: If holding selinexor does not resolve the neutropenia, consider holding/adjusting pomalidomide dose as described in Table 4, under Neutropenia.

The manufacturer of pomalidomide has provided dose adjustment guidelines for managing Grade  $\geq$  3 thrombocytopenia and neutropenia that occur during treatment in the package insert. These guidelines, together with the recommended dose adjustments provided in Table 4, should be consulted by the Investigator to manage thrombocytopenia and neutropenia associated with study treatments, as needed.

#### **7.7.2 Conditions Not Requiring Selinexor Dose Reduction**

The following conditions are exceptions to the dose-modification guidelines. Selinexor does not need to be held in the following cases:

- Alopecia of any grade
- Electrolyte or serum analyte (e.g., urate) abnormalities that are reversible with standard interventions. Treat hypokalemia and hypomagnesemia per institutional guidelines and repeat a 12-lead ECG to monitor the QTc as clinically indicated.

### **7.7.3 Selinexor Dose Reduction for Decreased Glomerular Filtration Rate**

Selinexor is not significantly eliminated by the kidney; therefore, no dose alteration of selinexor is required with renal dysfunction.

## **7.8 General Concomitant Therapy and Supportive Care Guidelines**

All concomitant medications will be recorded and/or updated on subject medication log throughout the course of the study and saved in subject binder, if applicable.

### **7.8.1 Required Anti-emetics: 5-HT3 Antagonists and Olanzapine**

In order to minimize nausea, anorexia and fatigue, unless contraindicated, all patients should receive serotonin receptor subtype (5-HT3) antagonists (ondansetron 8 mg or equivalent), starting Q8 hours before each dosing and continue 2-3 times daily for a few days (2-4 days) after dosing for the first 2 cycles, after which it may be tapered or discontinued as tolerated. Alternative antiemetic agents may be used if the patient does not tolerate or has inadequate antiemetic effect with 5-HT3 antagonists.

In addition, patients should receive olanzapine 2.5 mg PO daily starting on the evening prior to Day 1 and continuing for at least the first 2 months of the study. The dose of olanzapine can be increased as deemed necessary. The olanzapine dose may be dose reduced or stopped after 2 months of combination therapy period if nausea is well controlled. Please note that olanzapine can induce fatigue and should be discontinued in the case for fatigue grade >2.

Alternatives to olanzapine include:

- Megesterol Acetate - patients may receive megesterol acetate 80-400 mg daily, starting 1-3 days before the first dosing day of selinexor. In addition, megesterol acetate 80-400 mg daily may be added for any patients as part of general supportive care for anorexia.
- Mirtazapine 7.5-15 mg daily (QHS), starting 0-3 days in the evening before the first dosing day of selinexor. Please note that mirtazapine can induce fatigue and should be discontinued in the case for fatigue grade >2.

Avoid the use of strong CYP3A4 and/or CYP1A2 inhibitors (Appendix 1).

### **7.8.2 Supportive Care**

Supportive care guidelines for managing adverse events (AEs) are provided in Table 4.

Patients may receive other supportive care, including hydration prophylaxis, antibiotics, as appropriate.

Supportive care including additional anti-nausea/anti-emetic therapy, acid suppression (proton-pump inhibitors [PPI] and/or H2-blockers) and other treatments may be administered as follows:

- Appetite stimulants: megestrol acetate at a dose of 400-800 mg daily. Mirtazapine 15mg PO qPM can also be given
- Centrally acting agents: per *National Comprehensive Cancer Network® [NCCN] Clinical Practice Guidelines®*.

### **7.8.3 Infection Prophylaxis**

Patients will receive sulfamethoxazole/trimethoprim (800 mg/160 mg) PO three times weekly (i.e., Monday, Wednesday and Friday), or equivalent in case of allergy or intolerance. Patients considered by the Investigator to be at high risk for a bacterial infection should receive levofloxacin prophylaxis.

### **7.8.4 Glucocorticoid Side Effects**

The management of common glucocorticoid side effects is well documented. Aggressive use of PPIs, anti-hypertensives, glucose-lowering drugs and other agents is strongly encouraged in order to maintain the use of dexamethasone in combination with selinexor, clarithromycin and pomalidomide in this study.

Patients with documented osteopenia or osteoporosis should continue to take dexamethasone with selinexor as indicated in the study. Standard precautions such as use of antiresorptive therapy should be instituted unless contraindicated.

### **7.8.5 Non-study Related Concomitant Medication and Treatment**

Concomitant medications include any prescription or over-the-counter preparation, including vitamins, dietary supplements, over-the-counter medications, and oral herbal preparations taken during the study. Patients may continue their baseline medication(s), unless listed below under Restrictions or Prohibited Medications, as noted below. All concomitant medication(s) must be reported in the eCRF. Any diagnostic, therapeutic, or surgical procedure performed during the study period should be recorded, including the dates, description of the procedure(s), and any clinical findings, if applicable.

### **7.8.6 Prevention of pregnancy**

Patients should not become pregnant or father a child while on this study because the study treatments in this study can affect an unborn baby. Women should not breastfeed a baby while on this study. It is important that patients understand the need to use birth control while on this study. Female patients of childbearing potential must agree to use two methods of contraception (one highly effective and one effective) and have a negative serum pregnancy test at Screening and a negative urine test prior to receiving the first dose of study treatment, and male patients must use an effective barrier method of contraception if sexually active with a female of childbearing potential.

Highly effective methods include:

- Hormonal contraceptives (e.g., combined oral contraceptives, patch, vaginal ring, injectables, and implants)
- Intrauterine device or intrauterine system
- Vasectomy or tubal ligation

Effective methods include:

- Barrier methods of contraception (e.g., male condom, female condom, cervical cap, diaphragm, contraceptive sponge). Notes: No barrier method by itself achieves a highly effective standard of contraception. The proper use of diaphragm or cervical cap includes use of spermicide and is considered one barrier method. The cervical cap and contraceptive sponge are less effective in parous women. The use of spermicide alone is not considered a suitable barrier method for contraception. When used consistently and correctly, “double barrier” methods of contraception (e.g., male condom with diaphragm, male condom with cervical cap) can be used as an effective alternative to the highly effective contraception methods described above. Male and female condoms should not be used together as they can tear or become damaged.

Alternatively, the following fulfill the contraception requirements:

- A sexual partner who is surgically sterilized or post-menopausal.
- Total (true) abstinence (when this is in line with the preferred and usual lifestyle of the patient), is an acceptable method of contraception. NOTE: Periodic abstinence (e.g., calendar, ovulation, symptothermal, post-ovulation methods) and withdrawal are not acceptable methods of contraception.

For both male and female patients, effective methods of contraception must be used throughout the study and for 3 months following the last dose of study treatment. Please refer to the “Reproductive Risks” section above for additional safety information.

### **7.8.7 Thrombosis Prophylaxis**

Study participants should receive adequate prophylaxis for venous thromboembolism (VTE) depending on the thrombotic risk as assessed by the Investigator. Low VTE risk patients should receive aspirin 81 mg PO daily while receiving pomalidomide. Patients with multiple VTE risk factors (eg, previous VTE, known inherited thrombophilia, central venous catheter or pacemaker, severe cardiac disease, uncontrolled diabetes mellitus, prolonged immobilization, use of erythropoietin, obesity, chronic kidney disease [eGFR <30 mL/min], elevated D-dimer levels) should receive prophylactic or therapeutic dose low molecular weight heparin, warfarin or a non-vitamin K oral anticoagulant, rather than low-dose aspirin, while receiving pomalidomide.

### **7.8.8 Radiation Treatment**

If clinically indicated, palliative radiation therapy to non-target lesions is permitted but study drug should be held for  $\geq$  1 day before the start of palliative radiation therapy and  $\geq$  1 day following each dose of palliative radiation therapy. Treatment with selinexor shall not be discontinued solely due to palliative radiation.

### **7.8.9 Hematopoietic support**

Thrombocytopenia should be treated conservatively. In the absence of bleeding, platelet transfusions should only be given for a platelet count below 10,000/mm^3. If the patient develops bleeding, platelet transfusions should be administered in accordance with standard of practice, usually maintaining a platelet count  $\geq$  50,000/mm^3. Platelet growth factors may be used according to Table 4.

Treat anemia per institutional guidelines including blood transfusions and/or erythropoietin stimulating agents with concurrent anticoagulation as described above. Consider transfusing for hemoglobin  $<$  8 g/dL.

Granulocyte colony stimulating factors may be used for the management of neutropenia according to Table 4.

### **7.8.10 Prevention of skeletal related events**

Patients should receive osteoclast inhibitor therapy as deemed appropriate by the Investigator. Routine dental care is recommended.

### **7.8.11 Restrictions**

There are no restrictions on the use of acetaminophen or acetaminophen-containing products in combination with selinexor, except on days of selinexor dosing, when acetaminophen use must not exceed a total daily dose of 1 g.

Patients should not take any strong CYP3A4 and/or CYP1A2 inhibitors; please see Appendix 1 for a list of representative products. Patients should not take glutathione (GSH)-, S-adenosylmethionine (SAM)-, or N-acetylcysteine (NAC)-containing products during their participation in this study as these products may enhance the metabolism of selinexor. However, they are permitted if the patient has elevated liver function tests; please see Appendix 2 for a list of representative products.

Patients should not take drugs that are contraindicated with clarithromycin: colchicine, cisapride, pimozide, ergot alkaloids (e.g., ergotamine, dihydroergotamine), lomitapide, HMG-CoA reductase inhibitors extensively metabolized by CYP3A4 (e.g., lovastatin, simvastatin), saquinavir, midazolam (oral), ticagrelor, astemizole, domperidone, terfenadine, or ranolazine.

Prescribing Information for pomalidomide and dexamethasone should serve as a reference for potential restrictions and/or prohibitions.

There are no dietary restrictions in this study. Patients on selinexor should maintain adequate caloric and fluid intake.

### **7.8.12 Prohibited Medications**

Concurrent therapy with any approved or investigative anticancer therapeutic outside of those included in this study is not allowed. Use of any immunosuppressive agents during

the study must be confirmed by the Medical Monitor. The package insert should serve as a reference for potential restrictions and/or prohibitions. Avoid the use of strong CYP3A4 and/or CYP1A2 inhibitors (Appendix 1).

#### **7.8.13 Day one dosing guidelines**

On day one of study treatment, the patient will take:

- Selinexor 60 mg by mouth
- Clarithromycin 500 mg by mouth twice a day
- Pomalidomide 4 mg by mouth
- Dexamethasone 40 mg by mouth

Unless dose reduction is warranted due to renal and/or hepatic impairment, see section 7.7.1.

The patient will also be directed to take the following prophylactic medications:

- Aspirin 81 mg by mouth daily
- Omeprazole 20 mg by mouth (or equivalent) daily
- Ondansetron 8 mg by mouth (or equivalent) starting 8 hours before Selinexor dosing and continue 2-3 times daily for 2-4 days after dosing for at least the first 2 cycles.
- Olanzapine 2.5 mg by mouth every evening, starting on the evening before day 1 and continuing for at least the first 2 cycles.
- Trimethoprim-sulfamethoxazole 1 DS tablet by mouth three times per week (Monday, Wednesday, Friday).

Documentation of two negative pregnancy tests (serum hCG at Screening visit, and a urine pregnancy test on C1D1) is required prior to first dose in all female patients of childbearing potential.

#### **7.8.14 Instructions for initiation of a subsequent cycle**

A new course of treatment may begin on the scheduled day 1 of a new cycle if:

- Absolute neutrophil count (ANC)  $\geq$  1,000 cells/mm^3
- Platelets count  $\geq$  75,000/mm^3
- Any drug-related somnolence, rash, peripheral neuropathy, sinus bradycardia/other cardiac arrhythmia, allergic reaction/hypersensitivity, dyspepsia, gastritis, gastric or duodenal ulcer or confusion or mood alterations that may have occurred has resolved to  $\leq$  grade 1 severity.
- Any other drug-related non-hematologic adverse events that may have occurred have resolved to  $\leq$  grade 2 severity.

If these conditions are not met on Day 1 of a new cycle, the subject will be evaluated weekly and a new cycle of treatment will not be initiated until the toxicity has resolved as described above.

If the toxicity does not resolve within four weeks, the patient will be taken off the study. If the dosing of selinexor, clarithromycin, pomalidomide or dexamethasone was halted during the previous cycle and was restarted with a one-level dose reduction without

requiring an interruption for the remainder of the cycle, then that reduced dose level will be initiated on day 1 of the new cycle.

If the dosing of selinexor, clarithromycin, pomalidomide or dexamethasone was omitted for the remainder of the previous cycle or if the new cycle is delayed due to toxicity newly encountered on the scheduled day 1, then the new cycle will be started with dose modifications as described in Tables 3 and 4.

If the start of a new cycle is delayed more than 4 weeks, the patient will be taken off study.

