#### **7.7.1 Dosing Delays/Dose Modifications**

In order to optimize specific anti-tumor activity and tolerability, dose reductions and/or schedule modifications will be allowed. Patients should also be treated aggressively with supportive care to reduce toxicities. Doses must be adjusted for adverse events deemed related to study drug by the Investigator. Doses may be adjusted for adverse events related to study medications not listed below at the discretion of the Investigator.

Toxicity will be graded according to CTCAE v.5.0; the therapy modifications described below are to be applied according to severity grading. If more than one type of AE occurs concurrently, the most severe grade will determine the modification. Each dose modification or treatment delay must be documented, including the respective reason. Re-escalation of selinexor is allowed as outlined in Table 3. If drug-related toxicity requires a treatment delay of more than 28 days, the patient will be taken off study treatment. For all  $\geq$  Grade 3 hematological or non-hematological AEs that are NOT selinexor related, after consultation with the Medical Monitor and at the discretion of the Investigator, selinexor dosing may be maintained.

Table 3 summarizes the study treatment dose levels; Table 4 describes supportive care and dose adjustment guidelines. General supportive care recommendations are provided below. Deviations from the guidelines are permitted after discussion between the PI and the treating physician.

In patients with renal impairment, start each drug at the following dose level:

- 1) Selinexor:
  - (a) CrCl  $\geq$ 15 mL/min: There are no dosage adjustments provided in the manufacturer's labeling.
  - (b) CrCl <15 mL/min: Patients with severe renal impairment are excluded from this study.
- 2) Clarithromycin:
  - (a) CrCl  $\geq$ 30 mL/minute: No dosage adjustment necessary.
  - (b) CrCl 15-29 mL/minute: Decrease clarithromycin dose by 50% by starting at dose level -1.
  - (c) CrCl <15: Patients with severe renal impairment are excluded from this study.
- 3) Pomalidomide:
  - (a) CrCl  $\geq$ 15 to <60 mL/minute: There are no dosage adjustments provided in the manufacturer's labeling. Compared to patients with normal renal function, pomalidomide pharmacokinetics were not significantly altered in patients with CrCl between 15 to 60 mL/minute.
  - (b) CrCl <15 mL/min: Patients with severe renal impairment are excluded from this study.
- 4) Dexamethasone:

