	Grade 3 or 4	
Delay selinexor until resolved to Grade 1, then reduce selinexor dose by 1 dose level.
 
If diarrhea stabilizes for at least 4 weeks at Grade <math>\leq</math> 1, may re-escalate to previous dose of selinexor after consulting with the Medical Monitor.

Thrombocytopenia	Grade 1	Maintain dose.
	Grade 2 or 3 without bleeding	
Consider platelet growth factors, e.g., romiplostim, which may take up to four weeks for an effect.
 
Reduce selinexor at 1 dose level lower.
 
Patients with stable platelet counts for <math>\geq</math> 4 weeks following dose reduction may have their dose of selinexor increased by one dose level.

	Grade 4 without bleeding	Strongly consider platelet growth factors and transfuse per clinical practice/institutional guidelines. Delay dosing until recovery to $\leq$ Grade 2 or baseline and resume selinexor at 1 dose level lower.
	Grade 2 or 3 with bleeding	Delay dosing until the bleeding has stopped and the patient is clinically stable. Reduce selinexor at 1 dose level lower.
Neutropenia	Grade 3 or 4 Neutropenia without fever	Institute colony stimulating factors, and delay dosing with selinexor until ANC returns to Grade $\leq$ 2. Reduce selinexor by 1 dose level. After stabilization for at least 4 weeks, a re-escalation may be considered after discussing with the Medical Monitor.
	Grade 3 or 4 Neutropenia with fever	Institute colony stimulating factors, and delay dosing with selinexor until the patient's ANC returns to Grade $\leq$ 2 or baseline, fever has resolved, and patient's condition is stable. Reduce selinexor by 1 dose level.
Anemia	Grade 3	Treat per institutional guidelines including blood transfusions and/or erythropoietins. Consider transfusing for Hb $<$ 8 g/dL. Reduce selinexor by 1 dose level.
	Grade 4	Treat per institutional guidelines including blood transfusions and/or erythropoietins. Consider transfusing for Hb $<$ 8 g/dL. Delay dosing of selinexor until Hb is 8 g/dL or higher. Reduce selinexor by 1 dose level.
Ocular Toxicity	Grade 2, excluding cataract	Perform ophthalmologic evaluation. Interrupt selinexor and provide supportive care. Monitor until ocular symptoms resolve to Grade 1 or baseline. Restart selinexor at 1 dose level lower.
	Grade 3 or 4, excluding cataract	Permanently discontinue selinexor. Perform ophthalmologic evaluation.

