Generalized Muscle Weakness	Grade $\geq 3$	Reduce the dose of dexamethasone by 1 dose level, if symptoms persist, continue to reduce the dose of dexamethasone by 1 dose level as needed until toxicity has resolved to Grade $\leq 2$ .
Hyperglycemia	Grade $\geq 3$	Reduce the dose of dexamethasone by 1 dose level. Start insulin or other hypoglycemic therapy as needed.
Acute Pancreatitis	Grade $\geq 3$	Discontinue dexamethasone. Remove patient from study.
Other Dexamethasone-related Non-hematologic AEs	Grade $\geq 3$	Hold (interrupt) dexamethasone and follow weekly. If toxicity has resolved to Grade $\leq 1$ , restart dexamethasone at next lower dose level.
Pomalidomide		
	Onset day 1-14 of cycle	Onset <math>\geq</math> day 15 of cycle

	Grade 3 without fever	Maintain dose.	Maintain dose.
Neutropenia	Grade 3 with fever or Grade 4	Hold (interrupt) pomalidomide and follow CBC weekly. If neutropenia has resolved to Grade $\leq$ 2 prior to day 21, restart pomalidomide at next lower dose level and continue the cycle through day 21. If neutropenia is the only toxicity for which a dose reduction is required, G-CSF may be used and the pomalidomide dose maintained.	Omit pomalidomide for the remainder of cycle. See instructions for initiation of a new cycle and reduce the dose of pomalidomide by 1 dose level. If neutropenia is the only toxicity for which a dose reduction is required, G-CSF may be used and the pomalidomide dose maintained for the next cycle at the Investigators discretion.
	Grade 1 or 2	Maintain dose.	Maintain dose.
Thrombocytopenia	Grade 3 or 4	Hold (interrupt) pomalidomide and follow CBC weekly. If thrombocytopenia has resolved to Grade $\leq$ 2 prior to day 21, restart pomalidomide at next lower dose level and continue the cycle through day 21.	Omit pomalidomide for the remainder of cycle. See instructions for initiation of a new cycle and reduce the dose of pomalidomide by 1 dose level.
Non-blistering rash	Grade 3	Hold (interrupt) pomalidomide and follow weekly. If toxicity has resolved to Grade $\leq$ 1 prior to day 21, restart pomalidomide at next lower dose level and continue the cycle through day 21.	Omit pomalidomide for the remainder of cycle. See instructions for initiation of a new cycle and reduce the dose of pomalidomide by 1 dose level.
	Grade 4	Discontinue pomalidomide. Remove patient from study.	Discontinue pomalidomide. Remove patient from study.

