Desquamating (blistering) rash	Any grade	Discontinue pomalidomide. Remove patient from study.	Discontinue pomalidomide. Remove patient from study.
Neuropathy	Grade 3	Hold (interrupt) pomalidomide and follow weekly. If toxicity has resolved to Grade $\leq$ 1 prior to day 21, restart pomalidomide at next lower	Omit pomalidomide for the remainder of cycle. See instructions for initiation of a new cycle and reduce the dose of pomalidomide by 1 dose level.

		dose level and continue the cycle through day 21.	
	Grade 4	Discontinue pomalidomide. Remove patient from study.	Discontinue pomalidomide. Remove patient from study.
Thromboembolic event	Grade 3 or 4	Hold (interrupt) pomalidomide and start therapeutic dose anticoagulation. Restart pomalidomide at the Investigator's discretion maintaining dose level.	Omit pomalidomide for the remainder of cycle and start therapeutic dose anticoagulation.
Hyperthyroidism	Grade 3 or 4	Omit pomalidomide for the remainder of the cycle, evaluate etiology and initiate appropriate therapy. See instructions for initiation of a new cycle and reduce the dose of pomalidomide by 1 dose level.	Omit pomalidomide for the remainder of the cycle, evaluate etiology and initiate appropriate therapy. See instructions for initiation of a new cycle and reduce the dose of pomalidomide by 1 dose level.
Hypothyroidism	Grade 3 or 4	Omit pomalidomide for the remainder of the cycle, evaluate etiology and initiate appropriate therapy. See instructions for initiation of a new cycle and reduce the dose of pomalidomide by 1 dose level.	Omit pomalidomide for the remainder of the cycle, evaluate etiology and initiate appropriate therapy. See instructions for initiation of a new cycle and reduce the dose of pomalidomide by 1 dose level.
Other Pomalidomide-related non-hematologic AEs	Grade 1 or 2	Maintain dose. Initiate standard supportive care per institutional guidelines.	Maintain dose. Initiate standard supportive care per institutional guidelines.
	Grade 3 or 4	Hold (interrupt) pomalidomide and follow weekly. If toxicity has resolved to Grade $\leq 2$ prior to day 21, restart pomalidomide at next lower dose level and continue the cycle through day 21.	Omit pomalidomide for the remainder of the cycle. See instructions for initiation of a new cycle and reduce the dose of pomalidomide by 1 dose level.

All dose modifications should be based on the worst preceding toxicity.

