### **7.10 Duration of Follow Up**

Subjects will be followed for 12 months after end of treatment (EoT) visit or until death, whichever occurs first. Subjects removed from study for unacceptable adverse events will be followed until resolution or stabilization of the adverse event.

End of study will occur after the last patient to be enrolled has completed the one year follow up period, died, withdrawn consent, or been lost to follow up, whichever comes first.

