## **8. Study Intervention Discontinuation and Participant Discontinuation/Withdrawal**

### **8.1 Discontinuation of Study Intervention**

Discontinuation from study treatment does not mean discontinuation from the study, and remaining study procedures should be completed as indicated by the study protocol. If a clinically significant finding is identified (including, but not limited to changes from baseline) after enrollment, the investigator or qualified designee will determine if any change in participant management is needed. Any new clinically relevant finding will be reported as an adverse event (AE).

The data to be collected at the time of study intervention discontinuation will include the those outlined in the EoT visit as well as the Follow Up Phase.

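### The protocol contradicts itself on whether a toxicity stop ends treatment or study participation; one supportable reading ends PFS, DOR and OS follow-up in progression-free patients

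*Combined protocol and SAP*

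**What the plan says.** Some provisions end study participation:

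- Section 7.8.14 states it twice: "If the toxicity does not resolve within four weeks, the patient will be taken off the study", and "If the start of a new cycle is delayed more than 4 weeks, the patient will be taken off study".
- Table 4, pomalidomide rows for Grade 4 non-blistering rash, blistering rash of any grade and Grade 4 neuropathy: "Discontinue pomalidomide. Remove patient from study".
- Table 4, dexamethasone row for acute pancreatitis of Grade 3 or higher: "Discontinue dexamethasone. Remove patient from study".
- Section 8.2 allows the investigator to withdraw a participant from the study because of an adverse event.

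Others end treatment only, or keep the patient in follow-up:

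- Section 7.7.1: "If drug-related toxicity requires a treatment delay of more than 28 days, the patient will be taken off study treatment".
- Section 8.1: "Discontinuation from study treatment does not mean discontinuation from the study, and remaining study procedures should be completed". It also asks for the end-of-treatment (EoT) and follow-up data when treatment stops.
- Sections 7.9 and 8.2 follow every patient to progression, withdrawal of consent, death or loss to follow-up.
- Section 7.10 sets follow-up at 12 months after the EoT visit, or until death.
- Table 4, Grade 3 or 4 ocular toxicity: "Permanently discontinue selinexor", with no removal from the study.

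One further sentence in section 7.10 bears on both sides: "Subjects removed from study for unacceptable adverse events will be followed until resolution or stabilization of the adverse event". It names no disease or survival follow-up for these patients.

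Section 12.4.3 censors PFS drop-outs at their last assessment without evidence of disease, treats OS in the same manner, and censors DOR at the last assessment when no progression has been seen.

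**The concern.** A toxicity delay beyond 28 days, or four weeks, leads to two different outcomes depending on the section a site opens. Because section 8.1 separates leaving treatment from leaving the study, the removal wording in section 7.8.14 and Table 4 cannot safely be treated as shorthand for stopping treatment.

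A site that takes that wording at face value, and reads the adverse-event sentence in section 7.10 as the rule for removed patients, could close out someone who has not progressed. The three-monthly disease assessments and survival contacts would then not be made. The patients affected are those who could not tolerate a four-drug regimen for which section 7.7.1.1 itself anticipates overlapping toxicity. If their later risk differs from that of patients who stay on treatment, censoring them at removal is informative, and the Kaplan-Meier summaries no longer describe all treated patients. With 26 patients, a handful of removals is enough to show.

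**Working it through.** **1. Is data loss required or only possible?** Sections 7.7.1, 7.9 and 8.1 and the 12-month sentence of section 7.10 point to continued follow-up. Section 7.8.14, four Table 4 rows, the adverse-event sentence of section 7.10 and the investigator's power in section 8.2 allow a site to end it. No provision says which prevails. Loss is therefore possible under one supportable reading.

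**2. Primary endpoint.** The plan's own power figure reproduces. Summing Bin(18, p) over 7 to 18 stage 1 responses, times the chance of reaching 14 in 26, gives power 0.8004 at p = 0.60 (stated 0.8) and one-sided type I error 0.0377 at p = 0.35 (within the stated 0.05).

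- The denominator does not change: section 12.1 analyses everyone who received a dose, and section 8.2 does not replace treated patients.
- Only confirmation of a response is exposed. Appendix 4 needs two consecutive assessments but sets no minimum interval. Response is assessed on day 1 of each cycle from cycle 2, and the EoT visit repeats the myeloma laboratory tests.
- What remains at risk is a response first seen at or just before removal, or a patient whose EoT visit is missed. If all four drugs are held, the EoT window (14 days from last dose) closes before a four-week delay has run, so that visit could be late.
- The count itself is sensitive. If 5% of true responders went unconfirmed (an assumed figure), the effective rate would be 0.60 × 0.95 = 0.57 and power 0.70. The documents give no reason to expect that rate.

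**3. PFS illustration.** One input is from the plan: the median PFS of 12.2 months for pomalidomide-naive patients on selinexor, pomalidomide and dexamethasone (section 2.2.1), which fits inclusion criterion 7. The rest are assumptions:

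- exponential PFS, so λ = ln 2 / 12.2 = 0.0568 per month;
- a fraction f = 0.20 assigned a toxicity stop, uniform on 0.5 to 6 months;
- hazard multiplied by h after the stop.

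Chance of being event-free at the assigned stop: (e^(−0.5λ) − e^(−6λ)) / (5.5λ) = (0.9720 − 0.7111) / 0.3125 = 0.835. Expected number: 26 × 0.20 × 0.835 = 4.3 patients.

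With full follow-up, for t > 6 and h ≠ 1:

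S(t) = (1 − f)·e^(−λt) + f·e^(−hλt)·[e^(6(h−1)λ) − e^(0.5(h−1)λ)] / [5.5(h−1)λ]

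For h = 2 at t = 10.92: 0.8 × 0.5377 + 0.2 × 0.3492 = 0.4302 + 0.0698 = 0.500, so the median is 10.9 months.

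If these patients are censored at the stop, the remaining events follow the original hazard and the Kaplan-Meier median stays at 12.2. Full-follow-up medians at f = 0.20:

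| Hazard after stop | Full follow-up | Censored at removal |
|---|---|---|
| ×1 | 12.2 | 12.2 |
| ×1.5 | 11.5 | 12.2 |
| ×2 | 10.9 | 12.2 |
| ×3 | 10.2 | 12.2 |

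At ×2, the full-follow-up median is 11.5 with 10% stopping and 10.4 with 30%. Starting instead from the all-patient median of 10.4 months, 20% stopping and ×2 give 9.4.

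**The case against.** The best answer is that the protocol already settles the matter. Section 7.9, whose title covers criteria for removal from the study, lists unacceptable adverse events among the reasons to stop and then keeps all patients in follow-up. Section 8.2 repeats that. Section 8.1 asks for follow-up data after discontinuation, and section 7.10.2 directs three-monthly assessments at patients who have not progressed. On this view, off study is loose wording for off treatment, and the adverse-event sentence in section 7.10 adds to the 12-month rule before it.

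Most of this stands. A reader might infer that the protocol obliges sites to drop these patients, or that section 7.10 limits them to adverse-event follow-up. The documents do not support either: the section 7.10 sentence contains no word of limitation, and sections 7.9 and 8.2 speak of all patients. What the answer does not do is remove the conflicting instructions, which are the ones a site consults when toxicity occurs.

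It is also fair that PFS, DOR and OS are exploratory and untested, and that the shift is small against sampling error. Simulating 100,000 trials of 26 patients under the ×2 case with full follow-up, 95% of sample medians fall between about 6.3 and 18.0 months, against a shift of 1.3 (12.2 − 10.9). But the shift is systematic: it favours the regimen whenever the hazard rises after stopping, and the confidence interval does not reflect it.

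**Conclusion.** The wording conflict is certain. Its consequence is conditional: under one supportable reading, progression-free patients who stop for toxicity lose disease and survival follow-up, and the exploratory PFS, DOR and OS analyses censor them, possibly informatively. About 4 of 26 patients would be affected under the assumed 20% stopping rate. At that rate the reported PFS median would be too high by about 0.7 months (hazard ×1.5) to 2.0 months (×3), and by 1.3 months at ×2. The stopping rate, its timing and the later hazard are assumptions; with an unchanged hazard there is no bias.

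A reader might also infer that the 14-of-26 decision is seriously threatened. The documents do not support that: the denominator is fixed, and only responses first seen at or just before removal, or patients with a missed EoT visit, are exposed.

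**What to change.** Reconcile sections 7.7.1, 7.8.14, 7.10 and 8.2 and Table 4 on whether a toxicity stop ends treatment or study participation. No criterion for stopping any drug needs to change, and none is proposed.

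- In section 7.8.14 (both sentences), the four Table 4 toxicities and section 8.2, state that, whatever ends treatment, the EoT visit, the 30-day contact and the three-monthly disease and survival follow-up of section 7.10.2 continue, as sections 7.9 and 8.1 already provide. The exceptions are withdrawal of consent, death and loss to follow-up; disease assessments end at progression.
- In section 8.2, make clear that an investigator's decision to withdraw a participant for an adverse event does not by itself end this data collection. Without this, section 8.2 would still conflict with the amended text.
- In section 7.10, state that adverse-event follow-up is in addition to the 12-month follow-up.

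The cost is one wording amendment and a few more follow-up visits of a kind already in the Schedule of Activities. Assessments not made after a removal may not be recoverable, so the change is worth making early.
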